Official Title: Triple Combination of Fosaprepitant, Dexamethasone and Palonosetron Versus Combination of Dexamethasone and Palonosetron for the Prevention of Postoperative Nausea and Vomiting in Patients Undergoing Laparoscopic Gastrointestinal Surgery

NCT number: NCT04853147

Date of the document: 18/04/2021

This study is a single-center, randomised, controlled, double-blind, parallel-group clinical trial

Study design

Patients is randomized in a 1:1 ratio to receive either triple therapy or doublet therapy using computer-generated codes with randomly block sizes. Randomization is stratified based on the apfel score (3 or 4). Triple therapy is combined with fosaprepitant plus dexamethesone and palonosetron. doublet therapy is combined with placebo (normal saline) plus dexamethesone and palonosteron. The study drug is prepared by the nurses in anesthetic pharmacy who do not participate in this trail. Allocation is concealed from the investigators, patients and surgeons. Fosaprepitant and placebo were contained in identical intravenous infusion bags. Study drug or placebo infusion was initiated before anesthetic induction. Dexamethasone and palonosetron are injected at induction in both group.

Anaesthetic protocol

A standardized total intravenous anaesthetic protocol will be applied to all patients. General anaesthesia will be induced with intravenous administration of propofol, cisatracurium and remifentanil. The anesthesia will be maintained by propofol and remifentanil under monitoring of the bispectral index. Standard patient monitoring including ECG, pulse oximetry, capnography, blood pressure will be performed. Before skin incision, non-steroidal anti-inflammatory drug (NSAID) will be injected for preemptive analgesia. At the end of surgery, ropivacaine was used as local infiltration anesthesia around the wound and intravenous patient-controlled analgesia containing hydromorphone and NSAID will be connected to patients at the end of surgery.

Statistical analysis

The hypothesis of this study is that the proportion of participants with PONV for triple therapy will be significantly lower than that for doublet therapy. A sample size of 1154 patients will be selected on the basis of the following assumptions: (1) the proportion of participants with PONV is about 50% in doublet therapy and is

estimated to 40% in triple therapy, (2) $\alpha =0.05$, (3) power 90% and (4) missed follow-up rate 10%.

Subgroup analysis will be stratified by apfel score, surgical site, or age respectively.

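### Does the missing time window and event definition for PONV leave the trial's single test open to choice after the data are seen?

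*Combined protocol and SAP*

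**What the plan says.** The outcome appears in two places in the Statistical analysis section. The hypothesis is that "the proportion of participants with PONV for triple therapy will be significantly lower than that for doublet therapy". The sample size then assumes that "the proportion of participants with PONV is about 50% in doublet therapy" and is "estimated to 40% in triple therapy", with alpha 0.05, power 90% and 10% lost to follow-up, for 1154 patients in total.

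The abbreviation is expanded only in the official title: "for the Prevention of Postoperative Nausea and Vomiting in Patients Undergoing Laparoscopic Gastrointestinal Surgery".

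The document does not give a start or end point for counting events, a schedule of assessments or an assessor. It does not say whether nausea alone, retching or use of a rescue antiemetic counts. The word primary is not used; that this is the primary outcome is inferred from its being the only hypothesis and the basis of the sample size. The only other analyses named are subgroups by Apfel score, surgical site and age.

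**The concern.** PONV can be counted over shorter or longer periods, and as any symptom or as vomiting alone. Each choice gives a different binary variable, and two analysts who followed the text to the letter could test different ones. Blinding protects the recording of events, but it does not prevent a choice of definition once the code is broken. If the most favourable of several versions were reported as the main result, the false-positive rate would exceed 5%.

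Power is also involved. The 90% applies to the outcome whose control rate is 50%, and without a window a reader cannot judge whether 50% is realistic.

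**Working it through.** **1. The plan's own figure.** Inputs from the Statistical analysis section: p1 = 0.50, p2 = 0.40, alpha 0.05, power 0.90, loss 10%. Allocation is 1:1 (Study design). The plan does not state sidedness; two-sided is tried first.

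n per arm = [z(0.975)·√(2·p̄·(1−p̄)) + z(0.90)·√(p1(1−p1) + p2(1−p2))]² / (p1−p2)², with p̄ = 0.45

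- First term: 1.960 × √0.495 = 1.379
- Second term: 1.2816 × √0.49 = 0.897
- n = (2.276)² / 0.01 = 518.04, so 519 per arm
- 519 / 0.90 = 576.7, so 577 per arm and 1154 in total

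This matches the stated size exactly. A one-sided calculation gives 940. The sample size is therefore that of one two-sided comparison of one proportion at the full 5%, with no allowance for alternatives.

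**2. How alike rival definitions would be.** For an event with rate p1 nested within an event with rate p2, the correlation is √[p1(1−p2) / (p2(1−p1))]. Rates other than 50% are assumptions.

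| Nested pair | Correlation |
|---|---|
| 50% by one time, 55% by a later time | √(0.225/0.275) = 0.90 |
| 50% by one time, 60% by a later time | √(0.20/0.30) = 0.82 |
| Vomiting 25% within any PONV 50% | √(0.125/0.375) = 0.58 |

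**3. Error rate if the best of k were taken after unblinding.** Simulated null test statistics with equal correlation r, each tested at two-sided 0.05; k and r are assumptions.

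| r | Any false positive, k = 2 to 3 | In favour of triple therapy (nominal 2.5%) |
|---|---|---|
| 0.9 | 7.0% to 8.4% | 3.5% to 4.2% |
| 0.8 | 7.8% to 9.9% | 3.9% to 4.9% |
| 0.6 | about 8.8% to 11.8% | 4.4% to 5.9% |

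The hypothesis is directional, so the last column is closer to the harm feared. The bottom row depends on vomiting alone being a candidate, which fits poorly with a title that names nausea and vomiting together. For rival windows only, the first two rows apply.

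**4. Error rate if one definition is fixed beforehand.** A null simulation with 519 per arm assumed 40% PONV in a shorter window, 50% in a longer one, and vomiting in 35% of cases. The four candidate outcomes, each tested alone, had error rates of 5.1%, 5.1%, 5.0% and 5.0%. Picking the better of the two windows gave 7.8%. Picking the best of all four gave 13.6%, or 6.8% in favour of triple therapy. The excess comes from choosing late, not from which definition is used.

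**The case for a change.** The strongest case for acting is that this one document serves as both protocol and SAP, points to no other source for the definition, and leaves its only confirmatory test not uniquely determined. One label that covers several measurable variables is not one endpoint, and the title does not settle whether nausea alone, retching or rescue use counts.

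Power adds weight. With 519 per arm and the same 20% relative reduction (an assumption), power falls from 90% at a 50% control rate to about 77% at 40%, 59% at 30% and 49% at 25%.

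Part of this stands. The gap is real, and a reader cannot confirm from this document that the outcome was fixed in advance. The power figures are right, but they describe a trial that tests an outcome other than the one it was sized for. The plan uses the same term for the hypothesis and for the planning rates, so the natural reading is that the two coincide.

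What does not stand is the step from silence to permission. The plan lists no competing windows or endpoints and no rule for choosing among them. It shows neither that a choice was open to the investigators nor that one was made.

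**Conclusion.** No change follows. The document leaves the PONV window and the qualifying events unwritten, but no rule that it does state gives a wrong result. A sponsor that settles on one sensible definition before unblinding has a valid two-sided test at 5%. If that definition is the one to which 50% and 40% refer, the sample size stays at 1154 and power at 519 per arm stays at 90%.

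The inflation to about 7% to 12% two-sided, or about 3.5% to 6% in the favourable direction, needs two things that the document does not contain: two or three candidate outcomes with correlations of 0.6 to 0.9, and a choice among them after the results by arm are known. Writing the definition down would make the plan easier to check, but it would not alter the comparison, the alpha or the number of patients. Which definition to use cannot be settled from this document. The conclusion rests on reading the single hypothesis as the single confirmatory test, which the exact match of the sample size supports.

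### Age and surgical site are available at baseline but unused in the primary PONV comparison; adjusting for them would be an optional, nearly free and modest gain in precision

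*Combined protocol and SAP*

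**What the plan says.** In the combined protocol and SAP, the Statistical analysis section states the hypothesis that "the proportion of participants with PONV for triple therapy will be significantly lower than that for doublet therapy". The section names no test, model, effect measure or covariate for this comparison. The planned total of 1154 rests on the expectation that "the proportion of participants with PONV is about 50% in doublet therapy", against 40% with the triple combination, at alpha 0.05 with 90% power and 10% loss to follow-up.

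Under Study design, allocation is 1:1 and stratified by one factor only, the Apfel score (3 or 4).

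Age and surgical site appear once, in the closing sentence of the statistical section: "Subgroup analysis will be stratified by apfel score, surgical site, or age respectively". It follows that both will be recorded, at least for patients who enter the subgroup analyses. The documents do not list the surgical sites, say how patients divide among them, or say how strongly either factor relates to PONV.

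**The concern.** Two baseline variables are considered interesting enough to define subgroups, yet they have no part in the main comparison as described. Neither is a stratum, so neither is balanced by design. If either predicts PONV, a simple comparison of two proportions leaves that predictable variation in the error and makes no allowance for chance differences between the arms.

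An adjusted marginal risk difference targets the same quantity as the 50% versus 40% used for sizing. In large samples it is at least as precise as the crude difference. At stake is a somewhat narrower confidence interval and slightly more power from data already being collected. The validity of the trial is not in question.

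**Working it through.** **1. Reproduce the plan's sample size.** Inputs from the Statistical analysis section: p1 = 0.50, p2 = 0.40, alpha = 0.05 (sidedness not stated; two-sided assumed), power 90%, loss 10%. Allocation is 1:1 (Study design). The pooled two-proportion formula without continuity correction, with mean proportion 0.45, is

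n per arm = [1.960 × √(2 × 0.45 × 0.55) + 1.2816 × √(0.50 × 0.50 + 0.40 × 0.60)]² / 0.10²

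= (1.3790 + 0.8971)² / 0.01 = 518.04, rounded up to 519.

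Total evaluable = 2 × 519 = 1038, and 1038 / 0.9 = 1153.3, rounded up to **1154**. This matches the plan exactly. A one-sided test would give 940, and a two-sided test with continuity correction 1196. The stated N is therefore the unadjusted two-sided figure, and power at 519 per arm is 90.05%.

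**2. Precision without adjustment.** SE = √(0.25/519 + 0.24/519) = 0.0307, so the 95% CI half-width is 1.96 × 0.0307 = 6.02 percentage points.

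**3. Effect of adjustment.** The documents give no prognostic strength, so every odds ratio (OR) below is an assumption. All simulations use 519 evaluable patients per arm.

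*(a) Continuous age and a two-level site (50:50 split assumed), crude versus adjusted risk difference from a linear model with robust SE, 6,000 trials:*

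| Assumed ORs (age per SD; site) | Variance reduction | Power, crude to adjusted |
|---|---|---|
| Neither prognostic | none (ratio 1.002) | unchanged |
| 0.8; 1.3 | 1.8% | 90.4% to 91.1% |
| 0.7; 1.5 | 3.7% | 90.3% to 91.6% |
| 0.6; 2.0 | 7.3% | 89.7% to 91.8% |

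Type I error was about 5 to 6% for both analyses, the same within simulation noise.

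*(b) Two balanced binary factors, crude versus standardised logistic risk difference, 4,000 trials:* with ORs of 1, 1.5 and 2 for each factor, the variance ratios were 1.00, 0.99 and 0.96. Power (crude versus adjusted) was 89.0% versus 89.2%, 90.2% versus 90.7%, and 89.8% versus 91.8%.

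*(c) The analysis proposed below:* logistic standardisation with the Apfel stratum already in the model, so that only the increment from age and site is counted. From no prognostic value to the strongest assumed effects, the variance ratios v were 1.001, 0.984, 0.962 and 0.926. The estimated difference stayed at 10 points.

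**4. What those ratios are worth.** Half-width = 6.02 × √v. Patient equivalent = 1038 × (1/v − 1). Approximate power = Φ[(0.10 × √(519/v) − 1.3790) / 0.70], where 0.70 = √0.49. These use the step 2 variance as the base.

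| v | Half-width (points) | Patient equivalent | Power |
|---|---|---|---|
| 1 (reference) | 6.02 | 0 | 90.05% |
| 0.984 | 5.97 | about 17 | 90.5% |
| 0.962 | 5.91 | about 41 | 91.1% |
| 0.926 | 5.80 | about 83 | 92.1% |

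At v = 1.001 the loss is negligible.

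**The case against.** Four objections deserve weight.

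- **A reader might infer that the plan commits the trial to a crude analysis.** The documents do not say so. The hypothesis concerns proportions, and an adjusted marginal risk difference tests the same hypothesis. An unadjusted sample size does not bind the analysis either. All that can be said is that the comparison is described and sized without covariates and that the method is left open. This objection stands.
- **A reader might infer that precision is certainly being lost.** That requires age or site to predict PONV among patients with Apfel score 3 or 4, and the documents offer no evidence of this. Listing a factor for subgroup analysis shows interest in whether the treatment effect varies, not that the factor is prognostic. This stands too, so the gain is conditional and may be zero.
- **The Apfel stratum has the stronger, design-based claim to be in the model.** Agreed, and the proposed model includes it. Counting only what age and site add beyond Apfel leaves the range essentially the same (step 3c).
- **Chance imbalance in unstratified factors does not bias a randomised comparison, and with 519 per arm it should be small.** Correct. The case for adjustment is precision, not removal of bias.

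**Conclusion.** The point holds as an optional improvement that costs almost nothing. Age and surgical site will be available, are not strata, and play no stated part in the primary comparison. Adjusting for them would lower the variance by about 0 to 7%, raise power by about 0 to 2 points, and narrow the half-width from 6.02 to no less than about 5.8 points.

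These figures rest on assumed odds ratios, an assumed two-level site variable and 519 evaluable patients per arm. They illustrate a plausible range and do not predict the result.

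It would be wrong to conclude that the sample size is mistaken or the trial underpowered. The plan's own inputs reproduce 1154 and meet the stated 90% power. An unadjusted N is, if anything, slightly cautious when the analysis is adjusted.

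**What to change.** Add a short statement to the Statistical analysis section:

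- The primary estimate is the marginal risk difference in PONV (triple minus doublet) with a 95% CI.
- It is obtained by standardisation (g-computation) from a logistic model with treatment, Apfel stratum (3 or 4), age as a continuous term and surgical site, with a robust or delta-method standard error.
- Surgical site means the site planned before randomisation, with its categories listed.
- The covariates are fixed before unblinding.
- The crude difference in proportions is reported as a sensitivity analysis.

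N stays at 1154 and the target of estimation is unchanged. The cost is a few sentences of text and a few lines of code, with no extra patients, procedures or data beyond what the subgroup analyses already need. The one drawback is that the primary result is no longer read from a single two-by-two table, and the crude sensitivity analysis supplies that.

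### Does the missing rule for patients without a PONV outcome undermine the stated 90% power and 5% alpha?

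*Combined protocol and SAP*

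**What the plan says.** The Statistical analysis section states the hypothesis that "the proportion of participants with PONV for triple therapy will be significantly lower than that for doublet therapy". It continues: "A sample size of 1154 patients will be selected on the basis of the following assumptions". Those assumptions are that "the proportion of participants with PONV is about 50% in doublet therapy", with the other arm "estimated to 40% in triple therapy", alpha 0.05, and "3) power 90% and (4) missed follow-up rate 10" per cent. The only other analysis described is by subgroup: "Subgroup analysis will be stratified by apfel score, surgical site, or age respectively".

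The section does not say whether the proportion is taken over everyone randomised or everyone followed up. It does not say how a patient with no PONV assessment is classified, and it names no sensitivity analysis for missing outcomes. Under Study design, the trial is double-blind with 1:1 allocation, active drug and placebo come in matching bags, and "Allocation is concealed from the investigators, patients and surgeons".

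**The concern.** A plan that expects to lose one patient in ten on a binary primary outcome would normally say what happens to those patients. Three rules are in common use: leave them out, count them all as PONV, or count them all as free of PONV. They give different denominators, different event rates and sometimes different conclusions. If the rule is unwritten, it could be chosen once the results are known, and the stated power would be tied to an analysis nobody had committed to.

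A borderline case shows the stakes. Suppose 63 triple-therapy and 52 doublet patients are lost from 577 per arm, and the observed counts are 221/514 and 262/525.

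| Rule | Triple | Doublet | Difference (points) | Two-sided p |
|---|---|---|---|---|
| Observed only | 221/514 | 262/525 | -6.9 | 0.026 |
| Missing = PONV | 284/577 | 314/577 | -5.2 | 0.077 |
| Missing = no PONV | 221/577 | 262/577 | -7.1 | 0.014 |

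The same trial would be positive under two rules and negative under the third.

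**Working it through.** **Inputs from the Statistical analysis and Study design sections.** PONV 50% (doublet) and 40% (triple), alpha 0.05, power 90%, loss 10%, 1:1 allocation, total 1154 (577 per arm). The document does not state sidedness. A two-sided test reproduces 1154, whereas a one-sided test gives 940, so two-sided is used here.

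**Step 1: reproduce the sample size.** With pooled variance under the null,

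n = [1.960·√(2·0.45·0.55) + 1.282·√(0.5·0.5 + 0.4·0.6)]² / 0.10²

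= (1.379 + 0.897)² / 0.01 ≈ 518.0, rounded up to 519 per arm, or 1038 in total.

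Allowing for loss, 1038/(1 − 0.10) = 1153.3, rounded up to 1154. The match is exact. Dividing by 0.9 makes sense only if lost patients contribute no outcome and about 1038 observed outcomes carry the test.

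**Step 2: power under each rule.** Loss is 10% in each arm and unrelated to outcome. Power = Φ[(d − 1.960·SE₀)/SE₁], where SE₀ uses the pooled rate and SE₁ the separate rates.

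- Observed only, 519 per arm, 50% v 40%: SE₀ = 0.03088, SE₁ = 0.03073; (0.10 − 0.0605)/0.03073 = 1.28; power 90.1%.
- Missing = PONV, 577 per arm: the rates become 0.9·50% + 10% = 55% and 0.9·40% + 10% = 46%; (0.09 − 0.0577)/0.02932 = 1.10; power 86.5%. Reaching 90% would take 1294 patients.
- Missing = no PONV, 577 per arm: the rates become 45% and 36%; (0.09 − 0.0566)/0.02878 = 1.16; power 87.7%. Reaching 90% would take 1248 patients.

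**Step 3: alpha.** In 1,000,000 simulated trials (577 per arm, 50% in both arms, 10% random loss, pooled z test), each rule alone rejects in 4.8% to 5.0%. At least one of the three rejects in 7.6% two-sided, or 3.8% in favour of triple therapy against a nominal 2.5%. With 5% loss (an assumption) the two-sided figure is 6.9%.

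**Step 4: how often the choice matters.** The three rules disagree about a significant benefit in 10.5% of simulated trials at the planned 50% v 40%, and in 19.7% at 50% v 43%.

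**Step 5: robustness of the observed-outcome result.** Take 519 observed and 58 missing per arm, with 50% PONV among the missing doublet patients. Significance is lost once PONV among the missing triple patients reaches about:

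- 82% at an observed difference of −10 points (a 32-point gap between the missing groups)
- 64% at −8 points (a 14-point gap)
- 55% at −7 points (a 5-point gap)

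If the planned rates are true, an observed difference of 7 points or less has about a 16% chance: Φ[(0.07 − 0.10)/0.0307] = Φ(−0.98).

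**The case for a change.** The best case for changing the plan is that the implied rule is not a commitment. An all-randomised analysis with missing counted as PONV would contradict no sentence in the document, and it would run at 86.5% power instead of 90%. Unequal loss makes this sharper. With a true rate of 50% in both arms and an assumed 8% v 12% missing, either single-imputation rule rejects in about 10% of trials; at 5% v 15% the figure is about 40%. Even the observed-outcome rule is not immune. If 70% of the missing patients in one arm had PONV against 50% in the other, its false-positive rate is about 11%. Writing the rule down would cost only a sentence or two.

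Part of this stands: the rule is absent, and stating it before unblinding would be good practice. The argument does not show that the plan, followed as its own sizing implies, gives a wrong answer. With loss unrelated to outcome, the inflation of the two fixed-imputation rules under unequal loss is a defect of those rules, and the document proposes neither. Observed-outcome analysis stays at 5.0% in the same unequal-loss settings. The 11% figure needs loss that depends on outcome differently by arm, and naming a denominator would not remove that. Blinding, matching bags and concealed allocation make such loss less likely, though they cannot exclude it.

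The worked example is also a selected case. A loss gap of 2 points or more arises by chance in about 26% of trials (standard error √(2·0.1·0.9/577) = 1.77 points), but only about half of those put the excess in the triple arm. The observed difference must also fall near the significance boundary.

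**Conclusion.** No change follows. The document omits the denominator and the missing-outcome rule, but its arithmetic fits exactly one of the three usual choices: 1038 observed outcomes, divided by 0.9, give 1154. An analyst following that logic would compare observed outcomes in the assigned arms and have the stated 90% power at a 5% level. The loss of 2 to 4 points of power arises only if a rule is adopted that the document does not suggest. The rise to at most 7.6% among these three rules arises only from choosing between them after the results are seen, which is a matter of conduct and not of the stated design.

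A table of missingness by arm and a tipping-point analysis would be useful in the report, but they would correct no stated figure, rule or analysis. This conclusion assumes a two-sided test and loss near 10% that is similar in the two arms, or at least not tied to outcome differently by arm. Markedly unequal loss would call for scrutiny of the result under any rule.

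### Age is to be analysed by unspecified strata; if that means two bands, about 36–51% of the information on a linear change in benefit with age would be lost

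*Combined protocol and SAP*

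**What the plan says.** All the text on subgroups in the combined protocol and SAP is the sentence that closes the Statistical analysis section: "Subgroup analysis will be stratified by apfel score, surgical site, or age respectively". Age is given the same treatment as two categorical factors. Apfel score takes only the values 3 and 4 in this trial and is the randomisation stratum (Study design); age is not a randomisation factor.

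The documents do not give age cut-points, the number of age bands, an age distribution or age limits. They also name no interaction test, no model and no analysis with age on its continuous scale.

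The sample size rests on the overall comparison alone: "the proportion of participants with PONV is about 50% in doublet therapy" and "estimated to 40% in triple therapy", with 90% power, α = 0.05 and 10% lost to follow-up, giving 1154 patients. No figure is offered for any subgroup or interaction question.

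**The concern.** Stratifying by Apfel score or surgical site loses nothing, because those factors come in categories. Cutting age into bands removes the variation in age within each band. If the benefit of the third drug shifts gradually with age, that variation carries part of the evidence, and a formal test laid on top of the bands cannot recover it.

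Age is one of only three subgroup factors that the sponsor named, in a trial sized only for the overall difference. Power for effect modification is therefore scarce already. With no cut stated, the answer about older or younger patients would also depend on where the bands are drawn, a choice that could be made after the data are seen.

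**Working it through.** **Inputs from the documents (Study design; Statistical analysis).** PONV risk 0.50 (doublet) and 0.40 (triple), α = 0.05, power 0.90, 10% loss, 1:1 allocation, total 1154.

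**Assumptions, not in the documents.** The shape of the age distribution, the number and position of cuts, a linear change of effect with age, and the sizes of that change used below.

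**1. The plan's own figure.** Two-sided test with pooled variance and no continuity correction (sidedness is not stated, but two-sided reproduces the total):

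n per arm = [1.960·√(2·0.45·0.55) + 1.2816·√(0.50·0.50 + 0.40·0.60)]² / 0.10² = 518.04, rounded up to 519.

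Total 2 × 519 = 1038 evaluable; 1038/0.9 = 1153.3, rounded up to 1154. The stated total is reproduced, and 1038 is the evaluable number used below.

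**2. Information kept by two bands.** For a linear interaction, the share kept is the between-band variance of age divided by its total variance. For normal age cut at quantile q, with c = Φ⁻¹(q), this is φ(c)²/[q(1−q)].

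| Cut | Calculation | Kept | Lost | 1038 patients are worth |
|---|---|---|---|---|
| 50:50 | 0.3989²/0.25 | 0.637 | 36% | about 661 |
| 70:30 | 0.3477²/0.21 | 0.576 | 42% | about 598 |
| 80:20 | 0.2800²/0.16 | 0.490 | 51% | about 509 |

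For uniform age the losses are 25% (median), 37% (70:30) and 52% (80:20).

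**3. More than two equal bands, normal age.** With a trend scored at the band means, the shares kept are 0.793 (three bands), 0.861 (four) and 0.897 (five), so the losses are 21%, 14% and 10%. For uniform age they are 11%, 6% and 4%.

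An unscored heterogeneity test keeps the same shares but spends degrees of freedom. Take an interaction for which continuous age has 80% power: noncentrality (1.960 + 0.842)² = 7.85 on 1 df. Multiply by the share kept and read the power on the band test's df. Then find the 1-df noncentrality that gives the same power; its ratio to 7.85 is the equivalent fraction of patients.

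| Bands | Noncentrality | df | Power | Equivalent 1-df noncentrality | Equivalent loss |
|---|---|---|---|---|---|
| 2 | 5.00 | 1 | 61% | 5.00 | 36% |
| 3 | 6.23 | 2 | 60% | 4.91 | 37% |
| 4 | 6.75 | 3 | 57% | 4.59 | 41% |
| 5 | 7.04 | 4 | 54% | 4.27 | 46% |

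On the same basis, a scored trend across three bands has about 70% power and an 80:20 split 50%. A logistic simulation (N = 1038, 1,500 runs) agrees: 81% continuous, 59% median split, 49% at 80:20, 71% for a scored trend over tertiles and 60% for unscored tertiles.

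**4. What this means in risk differences.** Simulation with N = 1038 and risk = 0.5 − 0.03·age + t·(−0.10 + δ·age), where t = 1 for triple therapy and age is in SD units clipped at ±2.5, using a robust-SE test of the interaction:

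| δ per SD of age | Continuous | 50:50 | 70:30 | 80:20 |
|---|---|---|---|---|
| 5 points | about 37% | 25% | 23% | 20% |
| 8 points | about 74% | 55% | 50% | 44% |
| 10 points | about 90% | 74% | 69% | 61% |

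With no trend, the false-positive rate was about 5–5.6% for both approaches.

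**5. The opposite truth.** If the effect instead steps by 16 points exactly at the cut (an assumption), the order reverses. At a median step, power is about 55% for linear continuous age against about 74% for the matching bands; at an 80:20 step, about 30% against 55%.

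**The case against.** The strongest objection is that a reader might infer that the plan, as written, discards a third to a half of the information on age. The documents do not support this, because they fix neither the bands nor the test. Across the designs that the sentence allows, the loss under a linear interaction runs from about 4–10% (five equal bands, scored) to 66–73% (two bands split 10:90). The objection stands, and the loss has to be stated conditionally. It is softened by step 3: the plan names no trend score, and without one, using more bands brings back little power.

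Second, the calculations assume a linear change. Where the effect truly steps at the cut, banding is the better analysis. This also stands and is a real downside of a linear term.

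Third, the larger power gaps need strong interactions. With a mean effect of −10 points, a change of 8 or 10 points per SD removes the benefit at 1.25 or 1 SD from mean age, and nothing in the documents suggests that. At 5 points per SD, power is poor under either method, so the practical gain is smaller.

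Fourth, the plan promises subgroup analysis, not an age-trend test. Band-specific estimates are averages and do not in themselves assume a flat effect within a band. That is fair, and bands remain useful for display. Dependence on the cut is likewise partly a matter of pre-specification: fixing the cuts removes analyst discretion. It does not restore the information lost within bands, whereas a continuous analysis needs no cut at all.

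**Conclusion.** The point holds as a conditional, low-severity improvement. The plan commits to analysing age by strata and names no continuous-age analysis. If age is roughly normal and the effect changes roughly linearly with it, two bands cut between the median and 80:20 lose about 36–51% of the information on effect modification by age. Unscored tests over three to five equal bands cost a similar 37–46% in equivalent patients, at the point where continuous age has 80% power. A trend scored over three or four equal bands loses only 21% or 14%. Uniform age with a median split loses 25%, and a true step at the cut would favour banding.

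A reader might go further and infer that the trial's main result or its size is weakened. It is not: 1154 reproduces from the stated assumptions, and the primary comparison of PONV proportions does not use age bands. Only the exploratory age question is affected.

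**What to change.** Take age out of the list of stratified factors and add text along these lines: effect modification by age will be assessed with a treatment-by-age interaction, age continuous and linear, with a restricted cubic spline as a check on shape. The estimated difference in PONV risk and its 95% CI will be plotted across the observed age range. Estimates by age band, with cut-points fixed before unblinding, will be shown as description only. Apfel score and surgical site stay categorical.

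The cost is a short change to the subgroup text, one model and one plot, with no extra patients or data. The small downside is lower power of the linear term against a step or a non-monotone pattern, which the spline check and the displayed bands cover in part.
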